6.1.6. Pooling of Sites

Not Applicable.

6.1.7. Derived Variables

- MoCA Total score = sum of individual item scores, with a range from 0 to 30.

- D-KEFS Letter Fluency Total Correct Score = sum of F+A+S correct responses from 1-15, 16-30, 31-46, and 46-60 seconds.
- D-KEFS Category Fluency Total Correct Score = sum of Animals and Boys' Names correct responses from 1-15, 16-30, 31-46, and 46-60 seconds
- D-KEFS Category Switching Total Correct Score = sum of Fruits/Furniture correct responses from 1-15, 16-30, 31-46, and 46-60 seconds.
- D-KEFS Total Correct Score = sum of D-KEFS Letter Fluency Total Correct Score, Category Fluency Total Correct Score, and D-KEFS Category Switching Total Correct Score.
- MDS-UPDRS Part 1 score = sum of all Part 1 individual item scores. Part 1 consists of 13 items on a scale of 0 (normal) to 4 (severe), so the Part 1 score ranges from 0 to 52. If an individual item is missing, it will be imputed as the average score for that part.
- MDS-UPDRS Part 2 score = sum of all Part 2 individual item scores. Part 2 consists of 13 items on a scale of 0 (normal) to 4 (severe), so the Part 2 score ranges from 0 to 52. If an individual item is missing, it will be imputed as the average score for that part.
- MDS-UPDRS Part 3 score = sum of all Part 3 individual item scores. Part 3 consists of 33 items on a scale of 0 (normal) to 4 (severe), so the Part 3 score ranges from 0 to 132. If an individual item is missing, it will be imputed as the average score for that part.
- MDS-UPDRS Parts 1-3 total score = sum of Part 1, Part 2, and Part 3 scores. If any of the individual part scores are missing, the total score will be set to missing.
- CISI-PD total score = sum of the four individual item scores (motor signs, disability, motor complications, and cognitive status) rated 0 (not at all) to 6 (very severe or disabled), with a range of 0 to 24.
- PDQ-39 Mobility subscore = sum of 10 items in the Mobility domain (converted from a range of 0 [never] to 4 [always/cannot do at all] to a range of 0 to 100), divided by the maximum possible score on the scale and multiplied by 100.
- PDQ-39 Activities of Daily Living subscore = sum of 6 items in the Activities of Daily Living domain (converted from a range of 0 [never] to 4 [always/cannot do at all] to a range of 0 to 100), divided by the maximum possible score on the scale and multiplied by 100.
- PDQ-39 Emotional Well-Being subscore = sum of 6 items in the Emotional Well-Being domain (converted from a range of 0 [never] to 4 [always/cannot do at all] to a range of 0 to 100), divided by the maximum possible score on the scale and multiplied by 100.

- PDQ-39 Stigma subscore = sum of 4 items in the Stigma domain (converted from a range of 0 [never] to 4 [always/cannot do at all] to a range of 0 to 100), divided by the maximum possible score on the scale and multiplied by 100.
- PDQ-39 Social Support subscore = sum of 3 items in the Social Support domain (converted from a range of 0 [never] to 4 [always/cannot do at all] to a range of 0 to 100), divided by the maximum possible score on the scale and multiplied by 100.
- PDQ-39 Cognitions subscore = sum of 4 items in the Cognitions domain (converted from a range of 0 [never] to 4 [always/cannot do at all] to a range of 0 to 100), divided by the maximum possible score on the scale and multiplied by 100.
- PDQ-39 Communication subscore = sum of 3 items in the Communication domain (converted from a range of 0 [never] to 4 [always/cannot do at all] to a range of 0 to 100), divided by the maximum possible score on the scale and multiplied by 100.
- PDQ-39 Bodily Discomfort subscore = sum of 3 items in the Bodily Discomfort domain (converted from a range of 0 [never] to 4 [always/cannot do at all] to a range of 0 to 100), divided by the maximum possible score on the scale and multiplied by 100.
- PDQ-39 Total score = mean of all of the PDQ-39 subscores.
- GDS-15 Total score = sum of the 15 item questionnaire, with a range of 0 to 15. Each question is answered “yes” or “no”. Question numbers 1, 5, 7, 11, 13 indicate presence of depression when answered positively (yes) while the remaining questions indicate presence of depression when answered negatively (no). One point is counted for each depressive answer. A score of 0-4 indicates no depression, a score of 5-10 is suggestive of a mild depression, and a score of 11 or more is suggestive of severe depression.
- Modified Hachinski Ischemic Scale Total score = sum of the 8 item scores, with a range of 0-8.
- Change from baseline = value at current time point – value at baseline.
- TEAE = any adverse event with an onset date/time after first dose of medication.
- Disease duration (years) = [Enrollment date – PD onset date (as recorded on the Medical History case report form) + 1] / 365.25.

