7.1.1.3.9 Geriatric Depression Scale-15

The GDS-15 is a site-administered questionnaire of depression in older adults that will be read to the subject, and the answers will be recorded by the rater. The GDS-15 is a shortened form of a 30-item questionnaire in which participants are asked to respond by answering yes or no in reference to how they felt over the past week (Yesavage 1983)(Appendix 6). Questions from the long form GDS which had the highest correlation with depressive symptoms in validation studies were selected for the short version which is more easily used by mildly to moderately demented patients who have short attention spans and/or feel easily fatigued. Of the 15 items, 10 indicate the presence of depression when answered positively, while the rest (question numbers 1, 5, 7, 11, 13) indicate depression when answered negatively. It takes about 5 to 7 minutes to complete.

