Appendix 6. Geriatric Depression Scale-15

The GDS-15 is shortened form of a 30-item questionnaire in which participants are asked to respond by answering yes or no in reference to how they felt over the past week (Yesavage 1983). The GDS-S should be given orally. A clear YES or NO answer is required for each question. If necessary, repeat the question but do not accept a qualified answer from the test-taker. Cross off either yes or no for each question. Depressive answers (errors) are circled on the form and are bolded below. Count up 1 for each depressive answer (error). The final score is the tally of the number of depressive answers with the following scores indicating depression: 0-4 No depression, 5-10 Suggestive of a mild depression, and 11 + Suggestive of severe depression. For additional information, the full assessment can be downloaded using the following link: [Geriatric Depression Scale-15](#).

Geriatric Depression Scale – 15-Item Short Form		
Choose the best answer for how you have felt over the past week:		
1. Are you basically satisfied with your life?	YES	NO
2. Have you dropped many of your activities and interests?	YES	NO
3. Do you feel that your life is empty?	YES	NO
4. Do you often get bored?	YES	NO
5. Are you in good spirits most of the time?	YES	NO
6. Are you afraid that something bad is going to happen to you?	YES	NO
7. Do you feel happy most of the time?	YES	NO
8. Do you often feel helpless?	YES	NO
9. Do you prefer to stay at home, rather than going out and doing new things?	YES	NO
10. Do you feel that you have more problems with memory than most?	YES	NO
11. Do you think it is wonderful to be alive now?	YES	NO
12. Do you feel pretty worthless the way you are now?	YES	NO
13. Do you feel full of energy?	YES	NO
14. Do you feel that your situation is hopeless?	YES	NO
15. Do you think that most people are better off than you are?	YES	NO
Geriatric Depression Scale Total Score (number of bold answers circled)		

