8.2.8. Geriatric Depression Scale-15 (GDS-15)

The GDS-15 is a shortened form of a 30-item questionnaire in which participants are asked to respond by answering yes or no in reference to how they felt over the past week. Of the 15 items, 10 indicate the presence of depression when answered positively, while the rest (question numbers 1, 5, 7, 11, 13) indicate depression when answered negatively. Each item is recorded as yes or no which is assigned a numeric value of 1 or 0, respectively. The final score is the tally of the number of depressive answers with the following scores indicating depression:

- 0-4 No depression
- 5-10 Suggestive of a mild depression
- 11 + Suggestive of severe depression

Derivations for the final score is described in Section 6.1.7. The GDS-15 will be collected at Baseline (Visit 2), Week 8, (Visit 10) and Week 20 (Visit 18). The number and percentages of subject responses will be summarized by treatment group and visit. Change from baseline to study visit in GDS-15 total score will be summarized by treatment group.

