LS Mean Change from Baseline (SE) (95% CI for LS Mean Change from Baseline) P value for LS Mean Change from Baseline) [2]	XX.X (X.XX) (XX.X, XX.X) X.XXXX	XX.X (X.XX) (XX.X, XX.X) X.XXXX
LS Mean Difference from Placebo (SE) (95% CI for Difference from Placebo) P value for Difference from Placebo [3]		XX.X (X.XX) (XX.X, XX.X) X.XXXX

Abbreviations: ANCOVA = analysis of covariance; ApoE = apolipoprotein E; CI = confidence interval; LS = least squares; MoCA = Montreal Cognitive Assessment; SE = standard error.

Note: Higher scores indicate better cognitive function; the total possible score is 30 and a score of 26 or more is considered normal. A positive value of change means an improvement, and a negative value of change means deterioration. Subjects are summarized by randomized treatment.

[1] Estimates for LS means (change from baseline and difference from placebo [ie, change from baseline for GRF6021 minus change from baseline for Placebo]) and accompanying 95% CIs and P values are from an ANCOVA model with treatment, visit, and treatment-by-visit interaction as the main effects, and baseline MoCA total score, age, and ApoE genotype as covariates.

[2] P value for testing mean change from baseline is 0.

[3] P value for testing difference (GRF6021 minus Placebo) in mean change from baseline from is 0.

SOURCE: Listing 16.2.6.1

Statistical Analysis Plan,
Sponsor Alkermest, Inc.
Protocol Number ALK6021-201
PCN Number ALKA7951

Table 14.2.1.3
Summary of Change from Baseline in MoCA Total Score by Treatment
Per Protocol Set
(Same Shell as Table 14.2.1.1)

Table 14.2.1.4
Mean Change from Baseline in MoCA Score by Study Visit and Treatment
Tabulation of Fitted Summary Statistics from ANCOVA
Per Protocol Set
(Same Shell as Table 14.2.1.2)

Table 14.2.1.5
Summary of Change from Baseline in MoCA Total Score by Treatment
Complete Set
(Same Shell as Table 14.2.1.1)

Table 14.2.1.6
Mean Change from Baseline in MoCA Score by Study Visit and Treatment
Tabulation of Fitted Summary Statistics from ANCOVA
Complete Set
(Same Shell as Table 14.2.1.2)

Table 14.2.2.1
Summary of Change from Baseline in D-KEFS Scores by Treatment
Evaluable Set

Same Shell as Table 14.2.1.1

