Table 14.2.7.1
Summary of GDS-15 Categories by Study Visit and Treatment
Evaluable Set

Study Visit Category	Placebo (N=XX)	GRF6021 (N=XX)
Baseline [1]		
0-4 No depression	XX (XX.X%)	XX (XX.X%)
5-10 Mild depression	XX (XX.X%)	XX (XX.X%)
11 + Severe depression	XX (XX.X%)	XX (XX.X%)
Week 8 (Visit 10)		
0-4 No depression	XX (XX.X%)	XX (XX.X%)
5-10 Mild depression	XX (XX.X%)	XX (XX.X%)
11 + Severe depression	XX (XX.X%)	XX (XX.X%)
Week 20 (Visit 18)		
0-4 No depression	XX (XX.X%)	XX (XX.X%)
5-10 Mild depression	XX (XX.X%)	XX (XX.X%)
11 + Severe depression	XX (XX.X%)	XX (XX.X%)

Abbreviation: GDS-15 = Geriatric Depression Scale-15.
Note: Percentages are n/Number of subjects in the Evaluable Set*100. Subjects are summarized by randomized treatment.
[1] The baseline value is the SDS-15 assessment from Visit 2 or before.
SOURCE: Listing 16.2.6.7

Statistical Analysis Plan,
Sponsor Alkermes, Inc.
Protocol Number ALK6021-201
PCN Number ALKA7951

Table 14.2.7.2
Summary of Change from Baseline in GDS-15 Total Score by Treatment
Evaluable Set

(Same Shell as Table 14.2.1.1)

Programming Note: Parameter will be Total Score Visits will be Baseline (Visit 2), Week 8 (Visit 10), and Week 20 (Visit 18). Add GDS-15 to abbreviations. Update footnote to read "Note: Each item is recorded as yes or no which is assigned a numeric value of 1 or 0, respectively. The final score is the tally of the number of depressive answers with the following scores indicating depression: 0-4 No depression, 5-10 Suggestive of a mild depression, 11 + Suggestive of severe depression. [1] The baseline value is the PDQ-39 Score from Visit 2 or before." SOURCE: Listing 16.2.6.7.

Table 14.2.7.3
Mean Change from Baseline in GDS-15 Total Score by Study Visit and Treatment
Tabulation of Fitted Summary Statistics from ANCOVA
Evaluable Set

(Same Shell as Table 14.2.1.2)

Programming Note: Add GDS-15 to abbreviations. SOURCE: Listing 16.2.6.7.

Table 14.2.7.4
Summary of GDS-15 Categories by Study Visit and Treatment
Per Protocol Set

Same Shell as Table 14.2.7.1

Programming Note: Add GDS-15 to abbreviations. Update footnote to reflect Per Protocol Set. SOURCE: Listing 16.2.6.7.

Table 14.2.7.5
Summary of Change from Baseline in GDS-15 Total Score by Treatment
Per Protocol Set

Same Shell as Table 14.2.1.1

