Programming Note: Parameter will be Total Score Visits will be Baseline (Visit 2), Week 8 (Visit 10), and Week 20 (Visit 18). Add GDS-15 to abbreviations. Update footnote to read "Note: Each item is recorded as yes or no which is assigned a numeric value of 1 or 0, respectively. The final score is the tally of the number of depressive answers with the following scores indicating depression: 0-4 No depression, 5-10 Suggestive of a mild depression, 11 + Suggestive of severe depression. [1] The baseline value is the PDQ-39 Score from Visit 2 or before." SOURCE: Listing 16.2.6.7. Update footnote to reflect Per Protocol Set.

Table 14.2.7.6
Mean Change from Baseline in GDS-15 Total Score by Study Visit and Treatment
Tabulation of Fitted Summary Statistics from ANCOVA
Per Protocol Set

(Same Shell as Table 14.2.1.2)
Programming Note: Add GDS-15 to abbreviations. SOURCE: Listing 16.2.6.7.

Table 14.2.7.7
Summary of GDS-15 Categories by Study Visit and Treatment
Complete Set

Same Shell as Table 14.2.7.1
Programming Note: Add GDS-15 to abbreviations. Update footnote to reflect Per Protocol Set. SOURCE: Listing 16.2.6.7.

Table 14.2.7.8
Summary of Change from Baseline in GDS-15 Total Score by Treatment
Complete Set

Same Shell as Table 14.2.1.1
Programming Note: Parameter will be Total Score Visits will be Baseline (Visit 2), Week 8 (Visit 10), and Week 20 (Visit 18). Add GDS-15 to abbreviations. Update footnote to read "Note: Each item is recorded as yes or no which is assigned a numeric value of 1 or 0, respectively. The final score is the tally of the number of depressive answers with the following scores indicating depression: 0-4 No depression, 5-10 Suggestive of a mild depression, 11 + Suggestive of severe depression. [1] The baseline value is the PDQ-39 Score from Visit 2 or before." SOURCE: Listing 16.2.6.7. Update footnote to reflect Per Protocol Set.

Table 14.2.7.9
Mean Change from Baseline in GDS-15 Total Score by Study Visit and Treatment
Tabulation of Fitted Summary Statistics from ANCOVA
Complete Set

(Same Shell as Table 14.2.1.2)
Programming Note: Add GDS-15 to abbreviations. SOURCE: Listing 16.2.6.7.

Statistical Analysis Plan,
Sponsor Alkermes, Inc.
Protocol Number ALK6021-201
PCN Number ALKA7951

Table 14.2.8.1
Summary of Change from Baseline in dCDT Score by Treatment
Evaluable Set

(Same Shell as Table 14.2.1.1)

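### SAP 6.1.7 reverses the GDS-15 scoring key (15 minus the true total on complete forms), and the GDS-15 ANCOVA tables inherit a MoCA direction note that is wrong for the scale

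*SAP*

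**What the plan says.** Change from baseline in the GDS-15 is a named secondary efficacy endpoint (Protocol 4.2.2; SAP 2.2.2.2). The two documents contain three item codings.

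- **Reversed key.** SAP 6.1.7: "Question numbers 1, 5, 7, 11, 13 indicate presence of depression when answered positively (yes", and then "while the remaining questions indicate presence of depression when answered negatively (no". The footnote to Listing 16.2.6.7 (SAP 14.3) carries the same wording.
- **Correct key.** Protocol 7.1.1.3.9 says ten items point to depression on a positive answer, "while the rest (question numbers 1, 5, 7, 11, 13) indicate depression when answered negatively". SAP 8.2.8 words this identically.
- **Uniform coding.** SAP 8.2.8 and the notes to Tables 14.2.7.2, 14.2.7.5 and 14.2.7.8 add: "Each item is recorded as yes or no which is assigned a numeric value of 1 or 0, respectively".

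SAP 8.2.8 then refers the reader on: "Derivations for the final score is described in Section 6.1.7". Section 6.1.7, with the reversed key, is therefore the operative definition.

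On direction, the MoCA ANCOVA shell (Table 14.2.1.2, SAP 14.2) says higher scores are better, gives a maximum of 30 with 26 or more as normal, and adds: "A positive value of change means an improvement, and a negative value of change means deterioration". GDS-15 ANCOVA Tables 14.2.7.3, 14.2.7.6 and 14.2.7.9 use that shell. Their programming notes change only two things: "Add GDS-15 to abbreviations. SOURCE: Listing 16.2.6.7".

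**The concern.** Two sections of the SAP give mutually exclusive scoring rules, and the one that a programmer is told to use contradicts the protocol. The questions themselves settle which is right. Item 1 in Appendix 6 is "Are you basically satisfied with your life", and item 14 asks whether the situation feels hopeless. Under 6.1.7, a yes to item 1 and a no to item 14 would each add a depression point.

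At stake are the sign of a secondary endpoint and the labels in its category tables. The error would be hard to notice in the output: both keys give scores from 0 to 15, so a range check passes, and p-values do not change. A real improvement would appear as an equally significant worsening.

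**Working it through.** **Inputs.** One point per depressive answer, range 0 to 15, bands 0-4 none, 5-10 mild, 11 or more severe (SAP 6.1.7). The five items are 1, 5, 7, 11 and 13; the other ten are the rest.

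**Notation, all 15 items answered.** Let A be the number of yes answers among the five items and B the number among the other ten.

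- Protocol key: T = (5 − A) + B
- SAP 6.1.7 key: S = A + (10 − B)
- Uniform yes=1/no=0 coding, if summed: Y = A + B

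Both T and S run from 0 to 15, which reproduces the stated range.

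**Reversed against correct.** S + T = 15, so S = 15 − T. Enumerating all 2^15 = 32,768 complete answer patterns confirms this in every one.

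| True total T | True band | 6.1.7 score S | Tabulated band |
|---|---|---|---|
| 0 to 4 | none | 15 to 11 | severe |
| 5 to 10 | mild | 10 to 5 | mild |
| 11 to 15 | severe | 4 to 0 | none |

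In Tables 14.2.7.1, 14.2.7.4 and 14.2.7.7 the none and severe rows therefore swap, and the mild counts are unchanged.

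**Change from baseline.** (15 − T_post) − (15 − T_base) = −(T_post − T_base). Non-zero changes keep their size and reverse sign; zero stays zero. This affects the summaries in Tables 14.2.7.2, 14.2.7.5 and 14.2.7.8, whose notes describe the score as a count of depressive answers, so improvement would read as worsening.

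**ANCOVA and tests.** Replacing baseline b by 15 − b moves a constant into the intercept and reverses the baseline slope's sign relative to the outcome. Since the outcome is also reversed, the treatment coefficient changes sign only, with the same standard error and two-sided p-value. One simulated data set (assumed 68 subjects, 45 and 23 per arm; illustration only, not an estimate for this trial) gave −1.079 and +1.079 with p = 0.0178 both times, and a signed-rank p of 0.743 both times.

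**Key and direction note together**, when depression truly falls, in Tables 14.2.7.3, 14.2.7.6 and 14.2.7.9:

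| Key used | Note used | Sign of change | Reader is told |
|---|---|---|---|
| 6.1.7 | MoCA | positive | improvement (right by accident) |
| Protocol | MoCA | negative | deterioration (wrong) |
| 6.1.7 | GDS-15 | positive | deterioration (wrong) |
| Protocol | GDS-15 | negative | improvement (right) |

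Correcting only one of the two leaves these tables wrong. The 30 and 26 in the MoCA note are wrong for a 0-15 scale under either key.

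**Uniform coding.** Y − T = 2A − 5, which is odd and so never zero. Summing yes answers gives the wrong total on every complete form. A symptom-free form (A = 5, B = 0) has T = 0 but Y = 5, which falls in the mild band.

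**The case against.** The reversal itself cannot be explained away: nothing in the text suggests a redaction or extraction fault. The arguments on the other side concern weight and scope.

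- *Rank and recoverability.* The GDS-15 is one of nine secondary efficacy measures in a study not powered for efficacy. The correct key appears in the protocol and in SAP 8.2.8, the paper form has a total box, and item answers are listed, so scores can be recomputed. This limits the damage and makes it conditional on 6.1.7 being followed. It does not excuse the text: 6.1.7 defines the total as a derived variable, and nothing tells the programmer to use a site total.
- *Incomplete forms.* The SAP does not impute missing data and gives no GDS-15 missing-item rule. With k items answered, S = k − T: 12 answered and T = 2 gives 10, which is mild rather than severe. If k differs between visits, the sizes of change are not preserved either. This qualifier stands.
- *Percent change.* The MoCA summary shell heads its change column %CFB. If that meant percent change, size would not be preserved: T from 4 to 2 is −50%, while S from 11 to 13 is +18%. SAP 6.1.7 defines change as an absolute difference, so the % sign may be a slip.
- *Scope.* The same shell feeds the MDS-UPDRS and PDQ-39 ANCOVA tables (for example 14.2.3.2 and 14.2.6.2). Their programming notes do not replace the direction sentence either, although higher is worse on both scales. SAP 8.2.8 also describes no ANCOVA for the GDS-15; it appears only in the table list and shells. Both are further defects and do not weaken this point.

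**Conclusion.** The point holds and must be fixed before the GDS-15 is programmed. As written, the operative SAP derivation reverses the scale. For complete forms the score is exactly 15 minus the true total. Three category tables have their end rows swapped, three change summaries and three ANCOVA tables have the sign reversed, and the three ANCOVA tables also carry a direction note that is wrong for the correct key. The sizes of absolute changes and two-sided p-values are unaffected; direction and category labels are.

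This rests on three assumptions: that 6.1.7 is programmed as written, that all 15 items are answered, and that change is an absolute difference. The primary safety endpoint is not touched.

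**What to change.** 1. In SAP 6.1.7 and the Listing 16.2.6.7 footnote, score one point for no on items 1, 5, 7, 11 and 13 and one point for yes on the other ten, matching Protocol 7.1.1.3.9.
2. In SAP 8.2.8 and the notes to Tables 14.2.7.2, 14.2.7.5 and 14.2.7.8, delete the yes=1/no=0 sentence, or say that it is raw recording only and is not summed.
3. In Tables 14.2.7.3, 14.2.7.6 and 14.2.7.9, replace the inherited MoCA note with one saying that higher GDS-15 scores mean more depression and a negative change means improvement.

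Make items 1 and 3 in the same revision. While the shells are open, check the inherited note on the MDS-UPDRS and PDQ-39 ANCOVA tables too.

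The cost is a few lines of SAP text, one line of derivation code and the table notes named above. The item answers are already collected and listed, so any scores already derived can be recomputed, with no new data and no burden on patients.
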